10.11.10.6. Adverse Events, Serious Adverse Events, and Other Safety Reporting

See [Section 8.4](#).

10.11.10.7. Study Procedures

10.11.10.7.1. Visit A101 – Vaccination (Day 1)

Before enrollment and before any study-related procedures are performed, voluntary, written, study-specific informed consent will be obtained from the participant. Each signature on the ICD must be personally dated by the signatory. The investigator or their designee will also sign the ICD. A copy of the signed and dated ICD must be given to the participant. The source data must reflect that the informed consent was obtained before participation in the study.

It is anticipated that the procedures below will be conducted in a stepwise manner.

- Assign a participant number using the IRT system.
- Obtain the participant's demography (including date of birth, sex, race, and ethnicity). The full date of birth will be collected (as permitted by local regulations) to critically evaluate the immune response and safety profile by age.
- Obtain medical history data*, including confirmed COVID-19 diagnosis (see [Section 8.4.8](#)) or asymptomatic positive SARS-CoV-2 test result (NAAT or antigen test), and any other medical history of clinical significance.
 - *Include date of onset and resolution (if applicable).
- Perform a clinical assessment. If the clinical assessment indicates that a physical examination is necessary to comprehensively evaluate the participant, perform a physical examination and record any findings in the source documents and, if clinically significant, record on the medical history CRF or on the AE CRF as per [Section 10.3](#).
- Measure the participant's height and weight.
- Measure the participant's vital signs, including oral temperature, pulse rate, and seated blood pressure.
- Discuss contraceptive use as described in [Section 5.3.1](#).
- Review documentation of all prior COVID-19 vaccinations. Record prior receipt of any COVID-19 vaccine as described in [Section 10.11.8.7](#).
- Record details of any influenza vaccine received in the prior 12 months, as described in [Section 10.11.8.7](#).
- Record nonstudy vaccinations as described in [Section 10.11.8.7](#).
- Ensure and document that all of the inclusion criteria and none of the exclusion criteria are met.
- Ensure that the participant meets none of the temporary delay criteria as described in [Section 5.5](#).
- Obtain the participant's randomization number and study intervention allocation using the IRT system.
- Collect a blood sample (approximately 50 mL), before administration of study intervention, for immunogenicity assessment.

- Unblinded site staff member(s) will dispense/administer study intervention into the deltoid muscle of the arm as described in [Section 10.11.8](#). Please refer to the IPM for further instruction on this process.
- Site staff must observe the participant for at least 30 minutes after study intervention administration for any acute reactions. Record any acute reactions (including time of onset) in the participant's source documents and on the AE page of the CRF, and on an SAE form as applicable.
- Issue a measuring device to measure local reactions at the injection site and a thermometer for recording daily temperatures and provide instructions on their use.
- Explain the e-diary completion requirement to the participant and assist the participant with downloading the study application onto the participant's own device or issue a provisioned device if required. Provide instructions on e-diary completion and ask the participant to complete the reactogenicity e-diary from Day 1 through Day 7, with Day 1 being the day of vaccination.
- Ask the participant to contact the site staff or investigator immediately if they experience any of the following from Day 1 through Day 7 after vaccination (where Day 1 is the day of vaccination) to determine if an unscheduled reactogenicity visit is required:
 - Fever $\geq 39.0^{\circ}\text{C}$ ($\geq 102.1^{\circ}\text{F}$).
 - Redness or swelling at the injection site measuring greater than 10 cm (>20 measuring device units).
 - Severe pain at the injection site.
 - Any severe systemic event.
- Record AEs as described in [Section 8.4.1](#).
- Ask the participant to contact the site staff or investigator if a medically attended event (eg, doctor's visit, emergency room visit) or hospitalization occurs.
- Ask the participant to contact the site staff or investigator immediately if the participant experiences acute chest pain, shortness of breath, or palpitations (see [Section 10.11.10.7.5](#)).
- Schedule an appointment for the participant to return for the next study visit.
- Remind the participant to bring the e-diary to the next visit.
- Complete the source documents.

- The investigator or an authorized designee completes the CRFs and updates the study intervention accountability records.
- The investigator or appropriately qualified designee reviews the reactogenicity e-diary data online following vaccination to evaluate participant compliance and as part of the ongoing safety review. Daily review is optimal during the active diary period.

10.11.10.7.2. Visit A102 – 1-Month Follow-Up Visit (After Vaccination) – 28 to 35 Days After Visit A101

- Record AEs as described in [Section 8.4](#).
- Record nonstudy vaccinations as described in [Section 10.11.8.7](#).
- Record prohibited medication use as described in [Section 10.11.8.7.1](#).
- Verify understanding of and compliance with protocol requirements for contraception as described in [Section 5.3.1](#).
- Collect a blood sample of approximately 50 mL for immunogenicity testing.
- Review the participant's reactogenicity e-diary data. Collect stop dates of any reactogenicity e-diary events ongoing on the last day that the reactogenicity e-diary was completed and record stop dates in the CRF if required.
- If not already completed, collect the participant's e-diary or assist the participant with removing the study application from their own personal device.
 - Ensure all e-diary data have been transferred prior to e-diary deactivation or removal of the app.
- Record any AEs that occur within the 48 hours after the blood draw as described in [Section 8.4.1](#).

10.11.10.7.3. Visit A103 – 6-Month Telephone Contact – 175 to 189 Days After Visit A101

- Contact the participant by telephone.
- Record SAEs as described in [Section 8.4](#).
- Record nonstudy vaccinations as described in [Section 10.11.8.7](#).
- Record prohibited medication use as described in [Section 10.11.8.7.1](#).

- Complete the source documents.
- The investigator or an authorized designee completes the CRFs.

10.11.10.7.4. Unscheduled Visit for a Grade 3 or Suspected Grade 4 Reaction

If a Grade 3 local reaction ([Section 8.3.4.2](#)), systemic event ([Section 8.3.4.3](#)), or fever of $\geq 39.0^{\circ}\text{C}$ ($\geq 102.1^{\circ}\text{F}$) ([Section 8.3.4.4](#)) is reported in the reactogenicity e-diary, a telephone contact should occur to ascertain further details and determine whether a site visit is clinically indicated. If a suspected Grade 4 local reaction ([Section 8.3.4.2](#)), systemic event ([Section 8.3.4.3](#)), or fever ([Section 8.3.4.4](#)) is reported in the reactogenicity e-diary, a telephone contact or site visit should occur to confirm whether the event meets Grade 4 criteria.

A site visit must be scheduled as soon as possible to assess the participant unless any of the following is true:

- The participant is unable to attend the unscheduled visit.
- The local reaction/systemic event is no longer present at the time of the telephone contact.
- The participant recorded an incorrect value in the reactogenicity e-diary (confirmation of a reactogenicity e-diary data entry error).
- The PI or authorized designee determined it was not needed.

This telephone contact will be recorded in the participant's source documentation and the CRF.

If the participant is unable to attend the unscheduled visit, or the PI or authorized designee determined it was not needed, any ongoing local reactions/systemic events must be assessed at the next study visit.

During the unscheduled visit, the reactions should be assessed by the investigator or a medically qualified member of the study staff, such as a study physician or a study nurse, as applicable to the investigator's local practice, who will:

- Measure body temperature ($^{\circ}\text{F}/^{\circ}\text{C}$).
- Measure minimum and maximum diameters of redness (if present).
- Measure minimum and maximum diameters of swelling (if present).
- Assess injection site pain (if present) in accordance with the grades provided in [Section 8.3.4.2](#).

- Assess systemic events (if present) in accordance with the grades provided in [Section 8.3.4.3](#).
- Assess other findings associated with the reaction and record this on the AE page of the CRF if appropriate.
- The investigator or an authorized designee will complete the unscheduled visit assessment page of the CRF.

10.11.10.7.5. Additional Procedures for Monitoring of Potential Myocarditis or Pericarditis

Any study participant who reports acute chest pain, shortness of breath, palpitations, or any other symptom(s) that might be indicative of myocarditis or pericarditis within 28 days after study vaccination must be specifically evaluated for possible myocarditis or pericarditis.

In addition to a clinical evaluation, the following should be performed:

- ECG and
- Measurement of the troponin level

If myocarditis or pericarditis is suspected based upon the initial evaluation, the following should also be performed:

- Evaluation by a cardiologist,
- Cardiac echocardiogram and/or
- Cardiac magnetic resonance study

Details of the symptoms reported, and results of the investigations performed, will be recorded in the CRF.

10.11.11. Statistical Considerations – Substudy A

Methodology for summary and statistical analyses of the data collected in this substudy is described here and further detailed in the SAP, which will be maintained by the sponsor. The SAP may modify what is outlined in the protocol where appropriate; however, any major modifications of the primary endpoint definitions or their analyses will also be reflected in a protocol amendment.

10.11.11.1. Statistical Hypotheses

The estimands corresponding to the primary and secondary objectives are described in the table in [Section 10.11.5](#).

Both primary and secondary immunogenicity objectives are hypothesis-testing objectives. The subsections below describe details of hypotheses to be tested for each objective.

10.11.11.1.1. Statistical Hypotheses for Combined Vaccine Coadministered With QIV

A total of 8 hypotheses will be tested for the first primary immunogenicity objective as described below for each vaccine component.

1. The null hypothesis (H_0) to assess noninferiority of the response with respect to RSVpreF will be evaluated by the following hypothesis for both RSV A and RSV B as measured by NT:

$$H_0: \ln(\mu_1) - \ln(\mu_4) \leq \ln(0.5)$$

where $\ln(0.5)$ corresponds to a 2-fold margin for noninferiority, and $\ln(\mu_1)$ and $\ln(\mu_4)$ are the natural log of the geometric mean of NT at 1 month after vaccination for Group 1 and Group 4, respectively.

2. The null hypothesis (H_0) to assess noninferiority of the response with respect to BNT162b2 will be evaluated by the following hypothesis for both the SARS-CoV-2 Omicron BA.4/BA.5 strain and the reference strain as measured by NT:

$$H_0: \ln(\mu_1) - \ln(\mu_3) \leq \ln(0.5)$$

where $\ln(0.5)$ corresponds to a 2-fold margin for noninferiority, and $\ln(\mu_1)$ and $\ln(\mu_3)$ are the natural log of the geometric mean of NT at 1 month after vaccination for Group 1 and Group 3, respectively.

3. The null hypothesis (H_0) to assess noninferiority of the response with respect to QIV will be evaluated by the following hypothesis for each of the 4 strains included in QIV as measured by HAI titer:

$$H_0: \ln(\mu_1) - \ln(\mu_5) \leq \ln(0.5)$$

where $\ln(0.5)$ corresponds to a 2-fold margin for noninferiority, and $\ln(\mu_1)$ and $\ln(\mu_5)$ are the natural log of the geometric mean of HAI titers at 1 month after vaccination for Group 1 and Group 5, respectively.

10.11.11.1.2. Statistical Hypotheses for Combined Vaccine Alone

A total of 4 hypotheses will be tested for the second primary immunogenicity objective as described below for each vaccine component.

1. The null hypothesis (H_0) to assess noninferiority of the response with respect to RSVpreF will be evaluated by the following hypothesis for both RSV A and RSV B as measured by NT:

$$H_0: \ln(\mu_2) - \ln(\mu_4) \leq \ln(0.5)$$

where $\ln(0.5)$ corresponds to a 2-fold margin for noninferiority and $\ln(\mu_2)$ and $\ln(\mu_4)$ are the natural log of the geometric mean of NT at 1 month after vaccination for Group 2 and Group 4, respectively.

2. The null hypothesis (H_0) to assess noninferiority of the response with respect to BNT162b2 will be evaluated by the following hypothesis for both the SARS-CoV-2 Omicron BA.4/BA.5 strain and the reference strain as measured by NT:

$$H_0: \ln(\mu_2) - \ln(\mu_3) \leq \ln(0.5)$$

where $\ln(0.5)$ corresponds to a 2-fold margin for noninferiority and $\ln(\mu_2)$ and $\ln(\mu_3)$ are the natural log of the geometric mean of NT at 1 month after vaccination for Group 2 and Group 3, respectively.

10.11.11.1.3. Statistical Hypotheses for Coadministration of 3 Individual Vaccines

A total of 8 hypotheses will be tested for the first of the secondary objectives similar to [Section 10.11.11.1.1](#), except that Group 1 will be replaced with Group 7.

[figure not shown]
10.11.11.1.4. Statistical Hypotheses for Coadministration of 2 Individual Vaccines

A total of 4 hypotheses will be tested for the second of the secondary objectives similar to Section 10.11.11.1.2, except that Group 2 will be replaced with Group 6.

10.11.11.1.5. Multiplicity Adjustment

Type I error of 5% is equally split between the 2 primary immunogenicity objectives (2-sided 2.5% for each). The first primary immunogenicity objective will be achieved if all 8 null hypotheses are rejected. The second primary immunogenicity objective will be achieved if all 4 null hypotheses are rejected. The study is considered successful if either primary immunogenicity objective is achieved.

The secondary immunogenicity objectives will be tested sequentially after the primary objective(s) is achieved as described in the schema below.

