10.11.11.3.3. Secondary Endpoint(s)/Estimand(s) Analysis

Endpoint	Statistical Analysis Methods
Secondary immunogenicity	
 • GMRs of RSV A and RSV B NTs (Group 7 to Group 4), GMRs of SARS-CoV-2 Omicron BA.4/BA.5–strain NTs and reference-strain NTs (Group 7 to Group 3), influenza strain-specific GMRs of HAI titers (Group 7 to Group 5) at 1 month after vaccination will be provided with 97.5% CIs (Section 9.3.1.2.3). Using a 2-fold noninferiority margin, success for the first of the secondary immunogenicity objectives will be declared if the lower bound of the 2-sided 97.5% CI for the GMR is greater than 0.5 for both RSV A and RSV B antigens, for both the Omicron BA.4/BA.5 and reference strains, and for all 4 QIV strains, after the first primary immunogenicity objective is achieved. • GMRs of RSV A and RSV B NTs (Group 6 to Group 4) and GMRs of SARS-CoV-2 Omicron BA.4/BA.5–strain NTs and reference-strain NTs (Group 6 to Group 3) at 1 month after vaccination will be provided with 97.5% CIs (Section 9.3.1.2.3). Using a 2-fold noninferiority margin, success for the second of the secondary immunogenicity objectives will be declared if the lower bound of the 2-sided 97.5% CI for the GMR is greater than 0.5 for both RSV A and RSV B antigens and for both the Omicron BA.4/BA.5 and reference strains, after the second primary immunogenicity objective is achieved.

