10.11.11.5. Sample Size Determination

[Table 5](#) presents the power to demonstrate the noninferiority for each antigen included in Group 1 ([RSVpreF+BNT162b2] + QIV) as well as the power to demonstrate the noninferiority for each antigen included in Group 2 ([RSVpreF+BNT162b2] + placebo). The power for the secondary objectives is similar to that for the primary objectives as the comparisons and assumptions are similar.

For all assay results, no interference is assumed (ie, GMR=1). The SDs of the log titers are based on different reference studies. With 135 evaluable participants per vaccine group, there is ~90% power to declare noninferiority for all 8 antigens included in Group 1, and ~92% power to declare noninferiority for all 4 antigens included in Group 2. Power was calculated with PROC POWER in SAS using the TWOSAMPLEMEANS statement. Assuming 10% of the participants are nonevaluable, approximately 150 participants per group need to be enrolled for Groups 1 through 7.

Table 5. Power to Demonstrate Noninferiority (N=135 per Group)

Vaccine Component (SD Reference Study)	Antigen/Endpoint	Common SD (Log e Scale)	Difference (Log e Scale)	Noninferiority Margin	Power to Declare Noninferiority (1-Sided Alpha = 0.0125)
RSVpreF (C3671013)	RSV A NT	1.1	0	2-Fold	99.8%
	RSV B NT	1.1	0	2-Fold	99.8%
BNT162b2 (C4591044)	SARS-CoV-2 Omicron BA.4/BA.5–strain NTs	1.5	0	2-Fold	93.8%
	SARS-CoV-2 reference-strain NTs	1.3	0	2-Fold	98.3%
QIV (C3671006)	H1N1 HAI	1.1	0	2-Fold	99.8%
	H3N2 HAI	1.1	0	2-Fold	99.8%
	B strain 1 HAI	1.2	0	2-Fold	99.3%
	B strain 2 HAI	1.2	0	2-Fold	99.3%
Overall power to reject all 8 tests (Group 1 or 7 vs Group 4, Group 1 or 7 vs Group 3, Group 1 or 7 vs Group 5)					90.2%
Overall power to reject all first 4 tests (Group 2 or 6 vs Group 4, Group 2 or 6 vs Group 3)					91.8%

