5.1.5. Multiplicity Adjustment

Type I error of 5% is equally split between the 2 primary immunogenicity objectives (2-sided 2.5% for each). The first primary immunogenicity objective will be achieved if all 8 null hypotheses are rejected. The second primary immunogenicity objective will be achieved if all 4 null hypotheses are rejected. The study is considered successful if either primary immunogenicity objective is achieved.

The secondary immunogenicity objectives will be tested sequentially after the primary objective(s) is achieved as described in the schema below.

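### As far as the text shows, alpha is split between two testing chains and never released; two-way end-of-chain recycling would raise power on all four immunogenicity objectives at the same 5% familywise error

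*Protocol*

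**What the plan says.** The multiplicity rule is in protocol section 10.11.11.1.5 and is repeated in SAP section 5.1.5. "Type I error of 5% is equally split between the 2 primary immunogenicity objectives (2-sided 2.5% for each". Within each primary every component must succeed: "The first primary immunogenicity objective will be achieved if all 8 null hypotheses are rejected", and "The second primary immunogenicity objective will be achieved if all 4 null hypotheses are rejected". Either one is enough for the study: "The study is considered successful if either primary immunogenicity objective is achieved".

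For the secondaries, both documents refer to a schema: "The secondary immunogenicity objectives will be tested sequentially after the primary objective(s) is achieved". The schema is not shown in the text available to us. Protocol section 10.11.11.3.3 does spell out the gates. The Group 7 objective may be claimed only after the first primary, and the Group 6 objective only after the second.

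The decision level is fixed. Protocol section 10.11.11.3.2 sets a 97.5% CI for both primaries, and section 10.11.11.3.3 does the same for the secondaries: "success for the first of the secondary immunogenicity objectives will be declared if the lower bound of the 2-sided 97.5% CI for the GMR" exceeds 0.5 for every antigen, with matching wording for Group 6. SAP sections 6.1.1.1 and 6.1.2.1 present 97.5% CIs for the primaries, and SAP section 6.2 treats the secondaries alike. No visible passage allows a confirmatory decision on a 95% CI.

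**The concern.** The plan amounts to two chains, each holding one-sided 0.0125: first primary then Group 7 secondary, and second primary then Group 6 secondary. When one chain succeeds in full, its 0.0125 has no further use there. Under the written rule it is lost, and the other chain must still clear a 97.5% CI. A Bonferroni-based graphical procedure would pass it across.

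What is at stake is the chance of making the separate confirmatory claims: the combination with QIV, the combination alone, and the two coadministration schedules. Validity and the study success criterion are not at stake.

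**Working it through.** **Inputs** (protocol section 10.11.11.5 and Table 5): 135 evaluable per group; GMR = 1; margin ln 2 = 0.693; log-scale SDs of 1.1 and 1.1 (RSV A, RSV B), 1.5 (BA.4/BA.5), 1.3 (reference strain), 1.1 and 1.1 (H1N1, H3N2), 1.2 and 1.2 (B strains); one-sided alpha 0.0125. Correlations between antigens are not given, so they are assumptions here.

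**Step 1. Reproduce Table 5.** Per antigen, SE = SD × √(2/135), and power comes from the noncentral t with 268 df and noncentrality 0.693/SE. For BA.4/BA.5: SE = 1.5 × 0.1217 = 0.1826, noncentrality 3.80, critical t 2.254, power 93.8%, as stated. The others come to 99.8% (SD 1.1), 99.35% (SD 1.2) and 98.3% (SD 1.3). Multiplied as if independent, the 8 tests give 90.3% (stated 90.2%) and the 4 tests 91.9% (stated 91.8%). Table 5 is confirmed. With a full one-sided 0.025 the products would be 95.0% and 95.7%.

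**Step 2. Error control under recycling.** Proposed rule: start at 0.0125 per chain; if a chain succeeds in full, test the other at 0.0125 + 0.0125 = 0.025, in the same order.
- True nulls in one chain only: the first true null there is tested at no more than 0.025.
- True nulls in both chains: neither chain can release alpha until a false rejection has already occurred. The first error must therefore happen at 0.0125 in one of two chains, and the total is at most 0.0125 + 0.0125 = 0.025.

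A simulation of all 15 null configurations (2,000,000 trials) agrees. The largest one-sided error estimate was 0.0251, which is 0.025 within simulation error. The present rule gives about 0.012 when only one chain contains true nulls, so half the alpha goes unused there. Every rejection made at 0.0125 is kept, so no hypothesis loses.

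**Step 3. Power.** Simulation with Groups 3, 4 and 5 as shared comparators, GMR = 1. The correlated case assumes 0.8 within RSV, 0.7 within SARS-CoV-2, 0.3 within influenza and 0.1 between pathogens. Repeat runs differ by about 0.1 point.

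| Objective | Independent: present → recycled | Correlated: present → recycled |
|---|---|---|
| First primary (Group 1) | 90.6 → 93.8% | 91.4 → 94.3% |
| Second primary (Group 2) | 92.0 → 94.4% | 93.0 → 95.0% |
| Group 7 secondary | 83.5 → 89.1% | 85.2 → 90.3% |
| Group 6 secondary | 86.1 → 90.4% | 87.8 → 91.4% |
| All four | 75 → 85% | 78 → 87% |
| At least one primary | about 98%, unchanged | about 98%, unchanged |

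**Step 4. Sensitivity.** With one common correlation varied from 0 to 0.9, the gains in points are 2.2 to 3.2 (first primary), 1.9 to 2.4 (second primary), 4.0 to 5.7 (Group 7) and 3.4 to 4.3 (Group 6). At a common GMR of 0.9 and correlation 0.3 they are 6.0, 3.6, 9.3 and 5.9. At GMR 0.7 they are all below 0.3, because a chain is then rarely completed. Recycling in one direction only would help only the two objectives of the receiving chain.

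**Side observation.** Section 10.11.11.5 says: "The power for the secondary objectives is similar to that for the primary objectives". That holds for each secondary taken alone. Once the gate is counted, the written rule gives 83.5% and 86.1% with independent antigens.

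**The case against.** The strongest reply is that nothing here is wrong. A fixed split with gatekeeping is valid and simple to report, it matches the level used in Table 5, and it already gives each primary 90% or more. That stands, so this is an efficiency point. A reader might infer that type I error control or the sample size calculation is faulty; Steps 1 and 2 show neither.

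A reader might also infer that the study is less likely to succeed than it could be. The documents do not support that. Success means either primary, and recycling begins only after one primary has been met, so that probability does not move. For each primary alone the gain is only 2 to 3 points under the protocol's assumptions. The larger gains are for the secondaries and for all four objectives jointly, and the joint result is not a success criterion in the plan.

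The schema may already draw the recycling arrows, and its absence from our copy is not a defect. It would therefore be too strong to say that alpha is certainly discarded. Even so, the fixed 97.5% decision rules in protocol sections 10.11.11.3.2 and 10.11.11.3.3 would contradict such arrows, so the text needs attention either way. The SAP wording in 6.1 is weaker evidence, since it describes presentation rather than a decision.

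SAP section 6.3.5.2 already reports these GMRs with 95% CIs. Those are sensitivity summaries and do not support a confirmatory claim.

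Timing is a fair objection. The protocol lets the study team be unblinded after the 1-month analysis, and it cites sources accessed in October 2023. A threshold relaxed after results are known would not be credible.

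**Conclusion.** The point holds as an improvement that costs no power, and should be made if the timing allows. On the visible text, alpha is split 2.5%/2.5% and a completed chain's share is not released. Two-way recycling dominates this rule. At GMR = 1 it adds about 2 to 3 points for each primary and 3 to 6 points for each secondary, and with independent antigens it lifts the chance of all four from 75% to 85%. It adds nothing to the chance of at least one primary. The sizes rest on Table 5's SDs, 135 evaluable per group and assumed antigen correlations. The dominance and the error control do not depend on those assumptions.

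**What to change.** Before unblinding for the 1-month analysis, amend protocol sections 10.11.11.1.5, 10.11.11.3.2 and 10.11.11.3.3, and SAP sections 5.1.5, 6.1 and 6.2. The rule to add: if a primary and its own secondary both succeed with 97.5% CIs, the other primary, and then its secondary, are tested with 95% CIs (one-sided 0.025). The initial split, the order within each chain, the margin and the gates stay as they are. If the schema already shows these arrows, bring the fixed 97.5% wording into line with it instead.

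The cost is a protocol and SAP amendment, one more CI column in the tables, and a slightly longer explanation of the decision rule. No participants, samples or assays are added, and no objective loses power. If unblinding has already taken place, keep the written rule and treat any 95% CI result as descriptive.
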